- 4) Finally, the Overdose Prevention Kit will be shown to the patient. This involves a hands on demonstration of how to set up and administer the naloxone nasally, with the goal of subjects' learning this well enough to be able to use or teach significant others to administer naloxone to the subjects, if ever needed. The entire intervention is conducted in a Motivational Interviewing style of counseling. The interventionist will then summarize the conversation.

All interventions will be audio recorded if subjects permit, allowing the trainer/supervisor of the interventionists to monitor MI and overdose education fidelity throughout the course of the study.

Study Medication

The medication, naloxone, is being used for an indicated condition, opioid overdose. The specific formulation of Naloxone we plan to use is a 2mg/ml-2ml syringe that is made by International Medication Systems in El Monte, California (NDC # 00548336900).

The device used to deliver the medication nasally is a mucosal atomizer device (MAD300). The mucosal atomization device is licensed for intranasal atomization of prescription medications.

At usual doses, naloxone is relatively free of adverse effects. Because the duration of action of naloxone may be shorter than that of the narcotic being reversed, patients being treated for opioid intoxication with symptoms of respiratory depression should be closely monitored as additional doses of naloxone may be required. Administration of naloxone to opioid-dependent patients may provoke an acute withdrawal syndrome (including body aches, diarrhea, tachycardia, fever, runny nose, sneezing, piloerection, sweating, yawning, nausea or vomiting, nervousness, restlessness or irritability, shivering or trembling, abdominal cramps, weakness, and increased blood pressure). Withdrawal reaction are not life threatening. Agitation and paresthesia have been infrequently reported with the postoperative use of naloxone hydrochloride injection.

Hypersensitivity reactions, such as allergic reactions, are theoretically possible, but have never been documented with naloxone. We will ask about allergic reactions to naloxone during the baseline interview and at each of the three follow up interviews. Any allergic reactions will be reported to the University of Washington's human subjects division and the sponsor the National Institute on Drug Abuse.

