Study medication will be ordered, stored, maintained and dispensed by the Investigational Drug Service Pharmacies at Harborview Medical Center and UW Medical Center and the clinical dispensary at Evergreen Treatment Services. Upon receipt, the investigator, pharmacist, or authorized designee is responsible for taking inventory of the investigational agent. A record of this inventory will be kept and usage will be documented. Any unused or expired investigational agent shall be accounted for.

Adverse event reporting

The risks expected from trials employing behavioral interventions are presumed minimal and the medication being prescribed for possible future use is designed to be used to prevent a fatal overdose with side effects being rare. However, given the nature of ongoing drug and/or medication use the population studied in this trial is possibly at risk for an overdose. Adverse events (AEs) will be categorized as serious or non-serious, as related or not related to the study, and as expected or unexpected. An AE is defined as any reaction, side effect, or untoward event that occurs during the course of the clinical trial. Stable chronic conditions, such as substance abuse, which are present prior to clinical trial entry and do not worsen, are not considered AEs. Common, minor ailments and complaints will be excluded from any type of documentation. These may include: colds, flu's, cuts, scrapes, coughs, headaches, stomach complaints, and general fatigue.

Serious adverse events (SAEs) are defined as any fatal event, any immediately life threatening event, any permanent or substantially disabling event, any event that requires or prolongs inpatient hospitalization, congenital anomaly or birth defect, or any event requiring intervention to prevent any of the previously listed serious events. Hospital visits that do not result in admittance are not considered SAE's (e.g. emergency room visit for a non-study-related injury that does not result in admittance). Normal childbirth and pre-planned elective procedures are not considered SAEs. AE/SAE's will be elicited by interventionists/research interviewers at each assessment visit by asking the participants if they have noticed any new problems or existing problems that have gotten worse (using the Adverse Events Worksheet).

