Disclosure of an AE/SAE may also occur in an unsolicited manner to a research or clinical staff member. The interviewers should be focused on gathering data to aid in determining study relatedness. Study-relatedness will be determined by the interviewers in consultation with one of the investigators. All AEs and SAEs will be recorded in the AE/SAE log and entered into the secured project database. AEs that are not study related do not require any further paperwork documentation besides the AE Log. In this study, potential AEs that may be related to the study would be an increase in emotional distress in relation to discussion of past or current drug use behaviors *or side effects of naloxone*.

University of Washington Adverse Events reporting requirements

The term adverse event is generally used to refer to any untoward or unfavorable medical occurrence in a human subject, including any abnormal sign (for example, abnormal physical exam or laboratory finding), symptom, or disease, temporally associated with the subject's participation in the research, whether or not considered related to the subject's participation in the research. Adverse events encompass both physical and psychological harms. They occur

most commonly in the context of biomedical research although, on occasion, they can occur in the context of social and behavioral research.

Unanticipated problems, in general, include any incident, experience, or outcome that meets all of the following criteria:

1. unexpected (in terms of nature, severity, or frequency) given (a) the research procedures that are described in the protocol-related documents, such as the IRB-approved research protocol and informed consent document; and (b) the characteristics of the subject population being studied;
2. related or there is a reasonable possibility that the incident, experience, or outcome may have been caused by the procedures involved in the research; and
3. suggests that the research places subjects or others at a greater risk of harm (including physical, psychological, economic, or social harm) than was previously known or recognized.

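### The minor-ailment exclusion has no exception for symptoms after naloxone, so mild withdrawal symptoms can be left out of the adverse event log before relatedness is assessed

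*Combined protocol and SAP*

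**What the plan says.** The protocol's Adverse event reporting section defines an AE broadly enough to take in any reaction or side effect during the trial. It then sets an exclusion: "Common, minor ailments and complaints will be excluded from any type of documentation". The examples follow: "These may include: colds, flu's, cuts, scrapes, coughs, headaches, stomach complaints, and general fatigue". They are introduced as possibilities, so the list is open-ended, and no exception is made by cause, timing or naloxone exposure. AEs are elicited at each assessment by asking participants about new or worsening problems, using an Adverse Events Worksheet.

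The same section later says: "All AEs and SAEs will be recorded in the AE/SAE log and entered into the secured project database". It gives two kinds of AE that might be study-related: emotional distress from discussing drug use, and "side effects of naloxone".

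Study Medication states: "Administration of naloxone to opioid-dependent patients may provoke an acute withdrawal syndrome". Its symptom list begins "body aches, diarrhea, tachycardia, fever, runny nose, sneezing, piloerection, sweating, yawning, nausea or vomiting, nervousness, restlessness or irritability" and ends with four further entries: weakness, abdominal cramps, raised blood pressure, and shivering or trembling. The section adds that intranasal delivery usually produces milder withdrawal. It says participants will be asked about allergic reactions at baseline and at all three follow-ups, and that allergic reactions go to the university's human subjects division and the sponsor.

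The table under Schedule of and Sources Data Obtainment has one row for a negative or allergic reaction to naloxone and another for naloxone having been given to the subject. Both are listed among covariates and potential effect modifiers.

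**The concern.** One rule keeps common minor complaints out of all documentation. Another requires every AE to be logged and singles out naloxone side effects as possibly study-related. The main naloxone effect that the protocol describes is a withdrawal syndrome, and in mild form much of it resembles the excluded complaints. The protocol does not say which rule comes first when a participant reports such a complaint after receiving naloxone.

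The order matters. If the exclusion is applied at the interview, the complaint never reaches the step where the interviewer and an investigator decide on relatedness. It then cannot reach the oversight committee, which under Data monitoring is to review any adverse events. An event kept out of all documentation cannot be recovered later. What is at stake is how complete the non-serious safety record is for the one drug the study dispenses.

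**Working it through.** The plan gives no figure to reproduce, and no sample size or event-rate arithmetic applies. The check compares the two lists and then follows a complaint through the reporting steps.

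**Step 1: count the withdrawal entries.** The list in Study Medication has 12 entries in the run quoted above and 4 after it: 12 + 4 = 16.

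**Step 2: map each entry to the examples of excluded ailments.**

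- Stomach complaints: diarrhea; nausea or vomiting; abdominal cramps (3)
- Colds: runny nose; sneezing (2)
- Flu: fever; body aches (2)
- General fatigue: weakness (1)
- Arguable under flu: sweating; shivering or trembling (2)
- No matching example: tachycardia; piloerection; yawning; nervousness; restlessness or irritability; increased blood pressure (6)

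Plausible overlap: 3 + 2 + 2 + 1 = 8 of 16, or 50%. With the arguable entries: 8 + 2 = 10 of 16, or 62.5%. Total: 8 + 2 + 6 = 16. No entry appears word for word among the examples, so this tally is a matter of judgement and not a protocol figure.

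**Step 3: follow a mild complaint through the process.**

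- Follow-up is by phone at 3, 6 and 12 months (Follow-up Visits). The AE question is general, and the protocol describes no withdrawal checklist.
- A participant who mentions vomiting and a runny nose without mentioning naloxone gives the interviewer something that fits the exclusion.
- Relatedness is decided by interviewers with an investigator, but nothing says this is done before the exclusion is applied.
- Study Medication expects milder withdrawal with the intranasal route, so the expected presentation is also the one most easily judged minor.

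**Step 4: look for another route into the log.** The schedule's reaction row could catch these symptoms, since a negative reaction is wider than an allergic one. However, the text in Study Medication describes the question as covering allergic reactions only, and sends only those onward. No section connects a positive answer to the AE log, to the relatedness decision or to the committee.

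**The case against.** The best case for the plan is that the exclusion is aimed at background illness, and that the specific mention of naloxone side effects should prevail over a general sentence about colds and scrapes. This largely stands for a reaction that someone recognises: by the AE definition and the logging rule it is a loggable AE. It does not help with a symptom that is not recognised as following naloxone, because the protocol sets no order between the two rules.

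A reader might go further and infer any of three stronger points. The documents do not support them.

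- **That interviewers are told to record nothing about withdrawal.** A recognised naloxone reaction must be logged, the reaction row captures at least some of these events as study data, and at least 6 of the 16 entries match no excluded example.
- **That the loss favours the intervention arm.** Medics also give naloxone to overdose patients (Background and Rationale), and Other analyses anticipates that some standard-care subjects will obtain take-home naloxone. The exclusion applies to both arms, and no by-arm safety analysis is specified. A differential loss is possible but not established.
- **That the assumed overdose rates give the number of lost events.** They would count overdoses. Three further fractions are unknown: those given naloxone, those whose symptoms were only of the excluded kind, and those then set aside by the interviewer.

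Two more points stand. The Adverse Events Worksheet is not in the documents, so it may contain prompts that narrow the gap. The protocol also describes withdrawal reactions as not life-threatening, and mild, expected withdrawal would not meet its criteria for an unanticipated problem, which limits the seriousness of the omission.

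**Conclusion.** The concern holds as a conflict between stated rules. The exclusion has no exception for symptoms after naloxone and overlaps about half of the listed withdrawal entries (8 of 16; 10 on a broader reading). With a general elicitation question, mild withdrawal can be screened out before relatedness is considered, contrary to the rule that all AEs are logged. The interview item on naloxone reactions is a partial safeguard only, because it is not tied to the log and is described in two different ways.

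The effect is limited to the completeness of non-serious AE data, in either arm. Events meeting the SAE definition are not minor ailments and are unaffected, as are the primary outcome and the power calculation. The number of events lost cannot be estimated from the documents. The conclusion rests on two assumptions: that the mapping in the tally is reasonable, and that the worksheet does not already ask about symptoms after naloxone. The change is worth making before data collection, but the trial's main results do not depend on it.

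**What to change.** Reconcile Adverse event reporting, Study Medication and the schedule table on this point:

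- In Adverse event reporting, limit the minor-ailment exclusion to complaints that do not follow a naloxone administration since the last contact, whatever the source of the naloxone. The schedule already includes an item on naloxone given to the subject.
- State that any symptom reported after naloxone, including those in the Study Medication list, is entered in the AE log and assessed for relatedness.
- Have a positive answer to the reaction item open an AE log entry, and describe that item the same way in Study Medication (allergic only) and in the schedule (negative or allergic).

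The cost is about one sentence of protocol text, consistent wording for one question, and a REDCap link from existing items to the log. The downside is a few more minor AE entries to review.

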Source documents include all reports and records necessary for the evaluation and reconstruction of the clinical research study. The original recording of an observation should be retained as the source document. Because direct data entry through the REDCap electronic data capture system will be employed relatively few source documents are anticipated for the collection of primary data.

Data Safety Monitoring Oversight Committee

The Data Safety Monitoring Oversight Committee will have three representatives who have clinical and research expertise relevant to the study. They are not directly involved in the study. They will meet during the period of study planning, one month after the study is initiated and quarterly from then on. The committee will receive regular reports on the progress of the study, including the number and characteristics of subjects and those who declined to participate. Any serious adverse events (SAE) will be discussed with the committee to determine if the risks of SAE could be modified by any changes in study procedures. Other reports will be provided as the committee requests.

The committee will include two physicians: [name] a psychiatrist at the Veterans Affairs Puget Sound Health Care Network, where he is the medical director of addiction treatment services, he is also a Co-Investigator for medication studies for the Pacific Northwest Node of NIDA's Clinical Trials Network and conducts clinical trials and medical trainings on Suboxone- a medication which contains naloxone. The other physician member is [name] the director of HIV/STD programs for Public Health- Seattle & King County and Associate Professor of Medicine at the University of Washington. An additional committee member will have expertise in community based substance abuse treatment and the epidemiology of opioid abuse: [name], MSW is the director of Evergreen Treatment Services a methadone maintenance clinic serving more than 1,000 patients in the Seattle area, he is also the co-investigator for community treatment programs for the Pacific Northwest Node of NIDA's Clinical Trials Network.

Drug accountability

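### Two adjacent sentences on serious adverse events classify a life-threatening overdose released from the emergency department in opposite ways

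*Combined protocol and SAP*

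**What the plan says.** The section Adverse event reporting defines seriousness by a list of alternatives. It opens: "Serious adverse events (SAEs) are defined as any fatal event, any immediately life threatening event". It goes on to name, as its own item, "any event that requires or prolongs inpatient hospitalization", and closes with "any event requiring intervention to prevent any of the previously listed serious events". Only the hospitalization item depends on admission.

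The sentence that follows reads "Hospital visits that do not result in admittance are not considered" SAEs, with this illustration in parentheses: "e.g. emergency room visit for a non-study-related injury that does not result in admittance". A further sentence takes out normal childbirth and planned elective procedures.

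Three other statements bear on the point:

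- Data Safety Monitoring Oversight Committee: "Any serious adverse events (SAE) will be discussed with the committee", the purpose being to judge whether changed study procedures could modify the risk.
- Adverse event reporting: every adverse event, serious or not, goes into the log and the project database.
- Data monitoring: the committee's remit covers review of adverse events generally, not only serious ones.

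**The concern.** The exclusion carries no qualifier tying it to the hospitalization criterion, and it follows the whole list. Read as written, it removes events that the preceding sentence has just made serious on other grounds.

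In many trials this would be a small drafting matter. Here the disputed case is the event that the trial is about. Overdose is a primary outcome, and the adverse event section itself names it as a risk in this population. Background and Rationale reports that medics in Seattle gave naloxone about once a day in 2011 and that nearly all those patients were taken to the Harborview ED, which is a study site. The section Study Medication says that the training strongly encourages calling 911 at any suspected overdose. ED contact after an overdose is therefore foreseeable.

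What is at stake is consistency of safety classification: whether such an overdose is labelled serious, and whether it is assured a place in the committee's discussion of changing procedures.

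**Working it through.** The plan states no figure on this point, so the main check is textual.

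**Step 1. Is an overdose an adverse event at all?** Yes. The definition covers any untoward event during the trial. The carve-out for stable chronic conditions covers substance abuse that does not worsen, not an acute overdose. Nothing else exempts overdose.

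**Step 2. Apply the sentences to particular cases.**

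| Case | Definition alone | Exclusion read literally | Exclusion limited to the hospitalization criterion |
|---|---|---|---|
| Overdose, admitted | SAE | SAE (not excluded) | SAE |
| Life-threatening overdose, no hospital visit | SAE | SAE (not excluded) | SAE |
| Life-threatening overdose, reversed and released from the ED | SAE | Not an SAE | SAE |
| Fatal overdose in the ED before admission | SAE | Not an SAE | SAE |
| Minor injury meeting no serious criterion, released | Not an SAE | Not an SAE | Not an SAE |

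The third and fourth rows conflict. On the literal reading, a life-threatening overdose that never reaches a hospital is serious, while the same overdose treated in the ED and released is not.

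**Step 3. Does anything settle the conflict?** No section says which sentence prevails. The injury example is introduced as an example and does not limit the rule. The University of Washington reporting text turns on relatedness and unexpectedness, not on this seriousness rule. The plan says who judges relatedness (interviewers, in consultation with an investigator) but does not say who judges seriousness. Two staff members could each follow the protocol and label the same event differently.

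**Step 4. What depends on the label?** Logging does not, and neither does the committee's general review of adverse events. The SAE-specific discussion does.

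**Step 5. Size.** Inputs from Sample Size Calculation: 250 subjects per arm for each user type; annual control rates of 20% (heroin) and 10% (pharmaceutical opioids); a 50% reduction with the intervention. Applying that reduction to the annual pharmaceutical rate gives 5%.

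- Heroin: 250 × (0.20 + 0.10) = 75
- Pharmaceutical: 250 × (0.10 + 0.05) = 37.5
- Total: 75 + 37.5 = 112.5 subjects per year with any overdose

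The affected number is 112.5 × s, where s is the share whose overdose was life-threatening (or needed preventive intervention) and who were released from the ED. The documents do not give s. As assumptions for illustration only, s = 0.10 gives about 11 subjects a year and s = 0.50 gives about 56. The possible range runs from 0 to below 112.5.

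**The case against.** The best defence is that the exclusion was meant only to say that an ED visit is not a hospitalization. Several things support this. It turns on admission, which matters to that criterion alone. Its example is an unrelated injury. The sentence after it deals with childbirth and elective procedures, hospital stays that might otherwise meet that same criterion. The literal reading would also make a death in the ED before admission non-serious, which can hardly be intended. This is probably what the authors meant. The text does not say so, however, and staff classify by the text. If the narrow reading is intended, the fix merely states it.

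Three stronger readings are tempting and are not supported:

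- *A reader might infer that the committee would never see these overdoses.* Data monitoring gives it review of adverse events in general, every event is logged, and it can request other reports.
- *A reader might infer that the committee would miss an excess of overdoses in one arm because of this rule.* No section says that the committee receives events by arm, so the wording of this sentence neither creates nor removes that ability.
- *A reader might take 112.5 as the number of misclassified subjects.* It includes fatal overdoses, admitted cases that are SAEs on either reading, and overdoses that never reach a hospital.

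The primary overdose outcome is also untouched, since it is collected by interview and from administrative records whatever the safety label.

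**Conclusion.** The contradiction is real on the plain wording and should be corrected. A life-threatening overdose reversed and released from the ED is an SAE under the definition and not an SAE under the exclusion, with nothing to decide between them. The consequence is limited: such an event can be labelled non-serious, can miss the SAE-specific discussion of procedural changes, and can make SAE counts depend on the classifier.

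The conclusion about the wording rests on no numerical assumption. The number affected cannot be computed. The figure of 112.5 subjects a year is an upper pool that holds only at the plan's own rates and assumed 50% reduction, and it counts subjects rather than events.

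**What to change.** Reconcile the two sentences by limiting the exclusion to the hospitalization criterion. For example: *Hospital visits without admission do not by themselves meet the hospitalization criterion; the event is still an SAE if it meets another serious criterion.*

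This changes reporting classification only. It does not alter treatment, the primary outcome or the analysis. The cost is one sentence in the protocol and a few more SAE log entries.
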